### **7.5.1 Replacement of Subjects**

Subjects in Phase 1 will be considered nonevaluable for DLT and will be replaced if they do not experience a DLT and:

- they do not receive all infusions of both IMPs in Cycle 1 within 28 days at the doses assigned to the cohort in which they are enrolled, or
- they do not complete the safety follow-up through the end of the DLT evaluation period (Section [6.1.2.1](#)).

Subjects enrolled in Phase 2 may be replaced, for these same reasons, at the discretion of the Sponsor.

## **8 TREATMENTS**

### **8.1 Identity of Investigational Medicinal Products**

The Sponsor will provide both IMPs (mogamulizumab and nivolumab) to the investigational sites. Information about the IMPs to be used in the trial is summarized in [Table 8.1-1](#)

**Table 8.1-1 Identification of Investigational Medicinal Products**

Investigational Medicinal Product	Product Manufacturer	Concentration and Formulation as Supplied
[REDACTED]	[REDACTED]	[REDACTED]
[REDACTED]	[REDACTED]	[REDACTED]

iv=intravenous; USP=United States Pharmacopeia.

All IMPs will be labelled in an open-label fashion. Labels will bear the appropriate text as required by local regulatory requirements.

Guidance on the dilution procedures and recommended storage conditions for the diluted solutions of the IMPs can be found in the Pharmacy Manual.

Upon completion or termination of the study, all unopened containers of IMP must be destroyed at the site according to applicable regulations, institutional guidelines, and procedures, unless other arrangements have been approved by the Sponsor.

### **8.1.1     Treatments to be Administered**

The dose levels of the IMPs during the Phase 1 are described in [Table 6.1.1-1](#). The dosing schedules of the IMPs during the study are described in [Table 8.1.1-1](#).

**Table 8.1.1-1 Dosing Schedules of Mogamulizumab and Nivolumab During Phase 1 and Phase 2**

	Cycle 1				Cycle $\geq$ 2	
	Day 1	Day 8	Day 15	Day 22	Day 1	Day 15
Nivolumab	X		X		X	X
Mogamulizumab	X	X	X	X	X	X

Treatments will be administered on an outpatient basis. Each dose of IMP will be prepared by the pharmacy (refer to the Pharmacy Manual for full preparation, administration, and storage requirements). Mogamulizumab dosing calculations should be based on the body weight assessed at Cycle 1 Day 1 (baseline). Mogamulizumab dose adjustments for each cycle are required for greater than a 10% change in body weight.

All subjects will receive 240 mg of nivolumab as at least a 30-minute iv infusion on Days 1 and 15 of each 28-day cycle. When both nivolumab and mogamulizumab are administered at the same visit, the infusion of mogamulizumab will be started at least 30 minutes after the end of infusion of nivolumab.

- Nivolumab injection is to be administered as an iv infusion through a 0.2-micron to 1.2-micron pore size, low-protein binding polyethersulfone membrane in-line filter
- Subjects may be dosed no less than 12 days from the previous dose of nivolumab.
- There are no premedications recommended for nivolumab prior to the first infusion.

- Subjects should be carefully monitored for infusion-related reactions during IMP administration. If an acute infusion-related reaction is noted, subjects should be managed according to Section 8.2.2.

Subjects will then receive the cohort-assigned dose of mogamulizumab as at least a 1-hour iv infusion on Days 1, 8, 15, and 22 of the first cycle and on Days 1 and 15 of subsequent cycles.

- Mogamulizumab injection dose is to be administered as an iv infusion through a 0.22- or 0.2- $\mu$ m in-line filter.
- Subjects may be dosed no less than 5 days from the previous dose of mogamulizumab.
- Premedication with acetaminophen orally and diphenhydramine 50 mg iv (or equivalent) is recommended before the *first* mogamulizumab infusion (see Section 8.2.1).
- Subjects should be carefully monitored for infusion-related reactions during IMP administration. If an acute infusion-related reaction is noted, subjects should be managed according to Section 8.2.2.

Subjects should be closely monitored for AEs for at least:

- 30 minutes after the completion of the nivolumab infusion;
- 4 hours after the completion of the mogamulizumab infusion for the first 2 combination infusions (i.e., Cycle 1, Days 1 and 15); and
- 30 minutes after all other mogamulizumab infusions.

### **8.1.2 Dose Reduction and Dose Delay**

Doses of IMPs may be interrupted, delayed, or discontinued depending on how well the subject tolerates the treatment.

#### **8.1.2.1 Dose Reduction**

There will be no intra-patient dose reduction of either IMP by the Investigator. Doses within an assigned cohort may only be changed at the discretion of the SRC. (As of Amendment 3, the SRC will be disbanded.)

#### **8.1.2.2 Dose-delay Criteria**

IMP administration should be delayed for the following:

- Any Grade 2 or 3 IMP-related AE, with the following exceptions:
  - Grade 2 IMP-related fatigue or laboratory abnormalities do not require a treatment delay.
- Any Grade 3 IMP-related laboratory abnormality, with the following exceptions for lymphopenia or leukopenia, AST, ALT or total bilirubin or asymptomatic amylase or lipase:

- Lymphopenia or leukopenia of any grade does not require dose delay.
- If a subject has a baseline AST, ALT or total bilirubin that is within normal limits, delay dosing for drug-related Grade  $\geq 2$  toxicity.
- If a subject has baseline AST, ALT or total bilirubin within the Grade 1 toxicity range, delay dosing for IMP-related Grade  $\geq 3$  toxicity.
- If a subject has baseline AST, ALT, or total bilirubin within the Grade 2 toxicity range, delay dosing for IMP-related toxicity that increase by 2-fold or values  $> 8 \times \text{ULN}$ .
- Any Grade  $\geq 3$  IMP-related amylase or lipase abnormality that is not associated with symptoms or clinical manifestations of pancreatitis does not require dose delay. The Medical Monitor should be consulted for such Grade  $\geq 3$  amylase or lipase abnormalities. (As of Amendment 3, decisions regarding subject treatment should be made according to site standard of care as determined by the Principal Investigator.)
- Any AE, laboratory abnormality, or intercurrent illness which, in the judgment of the Investigator, warrants delaying the dose of study medication.

Subjects who require delay of IMP should be re-evaluated weekly or more frequently if clinically indicated and resume IMP dosing when re-dosing criteria are met.

### **8.1.3 Criteria to Resume Dosing**

Subjects may resume treatment with IMP when the drug-related AE(s) resolve(s) to Grade  $\leq 1$  or baseline, with the following exceptions:

- Subjects may resume treatment in the presence of Grade 2 fatigue.
- Subjects who have experienced Grade 3 drug-related skin AE must have improvement to Grade  $\leq 2$  within 3 days. Treatment may resume once the AE has improved to Grade  $\leq 1$ .
- Subjects who have experienced a Grade 2 drug-related skin AE may resume treatment when it has resolved to Grade  $\leq 1$ .
- Subjects with baseline Grade 1 AST/ALT or total bilirubin who require dose delays for reasons other than a 2-grade shift in AST/ALT or total bilirubin may resume treatment in the presence of Grade 2 AST/ALT OR total bilirubin.
  - Subjects with combined Grade 2 AST/ALT AND total bilirubin values meeting discontinuation parameters should have treatment permanently discontinued.
- Drug-related pulmonary toxicity must have resolved to baseline before treatment is resumed. Subjects with persistent Grade 1 pneumonitis (asymptomatic; clinical or diagnostic observations only, intervention not indicated) after completion of a steroid taper over at least 1 month may be eligible for retreatment if discussed with the Medical Monitor. (As of Amendment 3, decisions regarding subject treatment should be made according to site standard of care as determined by the Principal Investigator.)
- Drug-related endocrinopathies adequately controlled with only physiologic hormone replacement may resume treatment.

Dose delay of IMP for drug-related toxicity which results in treatment interruption of > 6 weeks requires treatment discontinuation, with the following exception:

- Dosing delays of > 6 weeks for prolonged steroid tapers to manage drug-related AEs are allowed. Re-initiation of treatment in a subject with a dosing delay lasting > 6 weeks from the previous dose requires consultation with the Medical Monitor. (As of Amendment 3, decisions regarding subject treatment should be made according to site standard of care as determined by the Principal Investigator.) Required protocol assessments should continue as per protocol even if dosing is delayed. Periodic study visits to assess safety and laboratory studies should also continue every 6 weeks or more frequently, if clinically indicated, during such dosing delays.

#### **8.1.4 Criteria for Treatment Discontinuation for Toxicity**

IMP treatment should be permanently discontinued if one or more of the following drug-related adverse events occurs:

- Any AE occurring at any time during treatment that is related to IMP and that meets the DLT criteria listed in Section 6.1.2.1, with the following exceptions:
  - Grade 2 pneumonitis which was treated and resolved according to the management guidelines in Section 8.2.3.
  - Grade 3 or 4 drug-related endocrinopathy AEs, such as adrenal insufficiency, adrenocorticotropic hormone (ACTH) deficiency, hyper- or hypothyroidism, or glucose intolerance, which resolve or are adequately controlled with physiologic hormone replacement (corticosteroids, thyroid hormones) or glucose-controlling agents, respectively, may not require discontinuation after discussion with the Medical Monitor. (As of Amendment 3, decisions regarding subject treatment should be made according to site standard of care as determined by the Principal Investigator.)
- Grade  $\geq 3$  hypersensitivity reaction or infusion-related reaction
- Any drug-related event that leads to delay in dosing lasting > 6 weeks from the previous dose requires discontinuation with the following exception:
  - Dosing delays of > 6 weeks for prolonged steroid tapers to manage drug-related AEs are allowed.
  - Re-initiation of treatment in a subject with a dosing delay lasting > 6 weeks from the previous dose requires consultation with the Medical Monitor. (As of Amendment 3, decisions regarding subject treatment should be made according to site standard of care as determined by the Principal Investigator.) Required protocol assessments should continue as per protocol even if dosing is delayed. Periodic study visits to assess safety and laboratory studies should also continue every 6 weeks or more frequently, if clinically indicated, during such dosing delays.
- Any AE, laboratory abnormality, or intercurrent illness which, in the judgment of the Investigator, presents a substantial clinical risk to the subject with continued IMP dosing.

### **8.1.5 Treatment Beyond Disease Progression**

The IMPs used in this trial are meant to induce an immune response against the subject's tumor and may not have an immediate effect on the tumor. In addition, the expected mechanism of action involves an infiltration of T-cells and inflammatory cells and local release of inflammatory cytokines. Therefore it is expected that initial radiographic progression may not be indicative of subsequent lack of response. Treatment may continue in spite of early radiographic progression, including appearance of new lesions, in the absence of symptomatic progression as long as the subject meets the other criteria in Sections 8.1.2 and 8.1.3 and has not had an AE that meets the criteria for treatment discontinuation in Section 8.1.4. Treatment past initial RECIST-defined radiographic progression may continue according to Investigator judgment, in consultation with the Medical Monitor, based on the subject's overall clinical status, overall tumor burden, and rate of progression, taking into account the subject's other treatment options and need for urgent intervention. (As of Amendment 3, decisions regarding subject treatment should be made according to site standard of care as determined by the Principal Investigator.) For example, a subject may continue treatment if a tumor assessment shows improvement or stable disease compared to the previous scan, even if there is progression compared to the baseline scan. Investigators may schedule an additional tumor assessment within 6 weeks after a scan showing progression, in order to reassess the subject's response.

Subjects may be treated after progression if they meet these criteria:

- Investigator-assessed potential clinical benefit;
- No disease-related clinical deterioration;
- Absence of progressive tumor at critical anatomical sites (e.g., cord compression) requiring urgent alternative medical intervention;
- Subject meets other re-dosing criteria in Section 8.1.3 and has not had an AE that meets the criteria for treatment discontinuation in Section 8.1.4.

If treatment is continued in spite of radiographic progression, the Investigator should record the rationale, and the subject must be informed that treatment beyond initial progression is not standard of care, and the Investigator should discuss potential risks and alternative treatment options. The sponsor will provide a consent form for re-consent of the subject prior to continuation of dosing, subject to institutional review board (IRB) approval.

Subjects should permanently discontinue study therapy upon evidence of further progression, defined as an additional 20% or greater increase in total measured tumor burden (TMTB) from time of initial progression. Total measured tumor burden should be determined as described in Section 9.2.6. The total measured tumor burden from time of initial progression

should be used as the reference baseline for comparison with the post-progression assessment.

### **8.1.6 Re-treatment for Progression during Follow-up**

Subjects who stop IMP without disease progression and who experience disease progression within 12 months of their last dose of IMP may receive additional IMP for up to 48 weeks provided that they meet the criteria in Sections 8.1.2, 8.1.3 and 8.1.4 and have not received other systemic therapy for their cancer. Biopsy of a progressing lesion should be obtained, if feasible. The Medical Monitor must be consulted before a subject in follow-up begins re-treatment. Subject must be re-consented prior to restarting IMP. (Upon implementation of Amendment 3, subjects who discontinued IMP without disease progression will not be allowed to receive additional IMP upon disease progression.)

The schedule of assessments for Cycle  $\geq 3$  should be followed, except that PK, PD, and anti-drug antibody (ADA) assessments are not required.

## **8.2 Management of Infusion-related Reaction and Other Toxicity**

### **8.2.1 Premedication**

It is recommended that subjects be premedicated with acetaminophen orally and diphenhydramine 50 mg iv (or equivalent), before the *first* mogamulizumab infusion. If a subject experiences an infusion-related reaction at any time during the study, pre-medication is recommended prior to subsequent infusions (see Section 8.2.2).

No premedications are recommended for nivolumab prior to first infusion. If a subject experiences an infusion-related reaction at any time during the study, pre-medication is recommended prior to subsequent infusions (see Section 8.2.2).

### **8.2.2 Treatment of Infusion-related Reactions**

As with any antibody, infusion-related reactions are possible. Appropriate drugs and medical equipment to treat allergic or anaphylactic reactions must be immediately available, and study personnel must be trained to recognize and treat infusion-related reactions. If a subject experiences an infusion-related reaction at any time during the study, premedication with the following medications is recommended prior to subsequent infusions: diphenhydramine 50 mg (or equivalent) and/or acetaminophen 325 to 1000 mg at least 30 minutes before additional IMP administration.

**All Grade 3 or 4 infusion-related reaction should be reported within 24 hours to the Sponsor (see Section 10.3.3.3).**

Treatment recommendations for infusion-related reactions are provided in [Table 8.2.2-1](#) and may be modified based on local treatment standards or guidelines, as appropriate. If a subject has an infusion-related reaction, blood samples should be drawn for assessment of cytokines ([Table 10.2-1](#)).

Cytokine-release syndrome is not expected with mogamulizumab or nivolumab, but if cytokine-release syndrome is suspected, consider use of cytokine antagonists such as tocilizumab (IL-6 receptor antagonist).

**Table 8.2.2-1 Recommended Management of Infusion-related Reaction**

Grade	Symptoms	Recommended Management
1/2	
 
Mild or Moderate (e.g., rash, flushing, urticaria, dyspnea, fever, pruritus/itching, rigors/chills, sweating [diaphoresis], tachycardia)
 
Moderate reactions may require therapy but respond promptly to symptomatic treatment (e.g., antihistamines, NSAIDS, narcotics, corticosteroids, bronchodilators, iv fluids)
 
	
 
The infusion rate of the IMP(s) should be temporarily interrupted until resolution of the event.
 
Acetaminophen, NSAIDS, antihistamines, narcotics, corticosteroids, bronchodilators, and iv fluids may be administered at the discretion of the Investigator.
 
The infusion should not be restarted until symptoms have subsided to Grade 1 or less.
 
The infusion may be re-started at half-rate when symptoms resolve. If no further complications ensue after 30 minutes, the rate may be increased full rate. If symptoms recur, then no further IMP should be administered at that visit.
 
Pre-medication prior to subsequent doses are recommended
 

3/4	
 
Severe/Life-threatening: Prolonged (i.e., not rapidly responsive to symptomatic medication and/or brief interruption of infusion); recurrence of symptoms following initial improvement; hospitalization indicated for other clinical sequelae (e.g., renal impairment, pulmonary infiltrates);
 
Pressor or ventilatory support indicated (i.e., bronchospasm, stridor, hypoxia, angioedema, swelling of lips, tongue, uvula, hypotension, abdominal pain, vomiting, hypoxia, syncope, collapse, incontinence).
 
	
 
Halt infusion immediately.
 
Begin iv infusion of normal saline.
 
Initiate treatment according to institutional standard of care including corticosteroids, epinephrine, cytokine antagonists, bronchodilators, intubation and respiratory support, iv hydration and vasopressors.
 
Discontinue IMPs.
 

IMP=investigational medicinal product; iv=intravenous; NSAIDS=non-steroidal anti-inflammatory drugs.

### **8.2.3 Immune-associated Select Adverse Events of Interest**

Immuno-oncology agents are associated with AEs that can differ in severity and duration than AEs caused by other therapeutic classes. Nivolumab and mogamulizumab are considered immuno-oncology agents in this protocol. Early recognition and management of AEs associated with immuno-oncology agents may mitigate severe toxicity.

Management algorithms have been developed to assist Investigators in assessing and managing the following groups of AEs and are included in the nivolumab IB:

- Gastrointestinal
- Renal
- Pulmonary
- Hepatic
- Endocrinopathies
- Skin
- Neurological

Recommended guidelines for managing hepatic events in subjects with elevated baseline LFTs are provided in Section [8.2.3.1](#).

For treatment of skin toxicity, recommended treatment guidelines are provided in [Table 8.2.3-1](#).

**Table 8.2.3-1 Recommended Management of Investigational Medicinal Product-related Dermatologic Toxicity**

Grade	Dermatologic AE
1	
Dosing delay is not required.
 
 
Initiate symptomatic therapy, e.g., antihistamines, topical or systemic corticosteroids (0.5 to 1.0 mg/kg/day methylprednisolone iv or oral, or equivalent), as needed.
 
 
If persists > 2 weeks, or recurs:
 
 
Consider skin biopsya;
 
Consider 0.5 to 1.0 mg/kg/day methylprednisolone iv or oral, or equivalent.
 

2	
 
Hold IMPs.
 
Initiate symptomatic therapy, e.g., antihistamines, topical or systemic corticosteroids (0.5 to 1.0 mg/kg/day methylprednisolone iv or oral, or equivalent), as needed;
 
 
If persists > 2 weeks or recurs:
 
 
Perform skin biopsya;
 
Consider 0.5 to 1.0 mg/kg/day methylprednisolone iv or oral, or equivalent. Once improving, taper steroids over at least 1 month, consider prophylactic antibiotics for opportunistic infections, and resume IMP.
 

3	
 
Hold IMPs until resolution to <math>\leq</math> Grade 1 or baseline grade.
 
Discontinue IMP if does not resolve to <math>\leq</math> Grade 2 within 3 days of the initiation of maximal supportive care.
 
Perform skin biopsya;
 
Dermatology consult;
 
1.0 to 2.0 mg/kg/day methylprednisolone iv or equivalent iv. Once improving, taper steroids over at least 1 month, consider prophylactic antibiotics for opportunistic infections, and resume IMP.
 

4	
 
Discontinue IMPs;
 
Perform skin biopsya;
 
Dermatology consult;
 
1.0 to 2.0 mg/kg/day methylprednisolone iv or equivalent iv. Once improving, taper steroids over at least 1 month, consider prophylactic antibiotics for opportunistic infections.
 

a: Skin biopsy may be submitted to central laboratory.

AE=adverse event; IMP=investigational medicinal product; iv=intravenous.

### 8.2.3.1 Recommended Management of Hepatic Events in Subjects with HCC

Subjects with advanced HCC generally have underlying cirrhosis with decreased hepatic function. They may also have a concomitant chronic viral infection. For the HCC cohort of this study, the upper limits for inclusion account for baseline liver dysfunction and allow enrollment of subjects with AST or ALT elevations within the CTCAE Grade 2 range. For these subjects, the following guidelines are provided:

- Dose delay criteria for hepatic events are outlined in Section 8.1.2.2. If AST or ALT levels do not improve with a dose delay of 3 - 5 days or if the levels worsen, initiate steroid therapy at 0.5 - 2 mg/kg/day methylprednisolone or oral equivalent.

- For ALT or AST levels  $> 8 \times \text{ULN}$ , initiate steroid therapy promptly at 1 - 2 mg/kg/day methylprednisolone or oral equivalent.
- For all subjects initiating steroids, consult the Medical Monitor within 24 hours after initiation of steroids. Gastroenterology consult is recommended. If AST or ALT levels do not improve within 3 - 5 days or the levels worsen after the start of steroid therapy, discuss with the Medical Monitor the possibility of adding mycophenolate mofetil at 1 g BID. (As of Amendment 3, decisions regarding subject treatment should be made according to site standard of care as determined by the Principal Investigator.)
- Tapering of steroids can start once AST or ALT levels have declined by 1 CTCAE grade. Taper steroids slowly over no less than 1 month.
- IMP may resume when AST or ALT have returned to near baseline unless the criteria for permanent discontinuation are reached (Sections 4.1.19 and 4.2). The Medical Monitor must be consulted prior to resuming IMP for all subjects who required steroid intervention. (As of Amendment 3, decisions regarding subject treatment should be made according to site standard of care as determined by the Principal Investigator.)
- Discontinue IMP for any drug-related liver function test (LFT) abnormality that meets the following criteria:
  - AST or ALT  $> 10 \times \text{ULN}$  for  $> 2$  weeks,
  - AST or ALT  $> 15 \times \text{ULN}$  irrespective of duration,
  - T. bilirubin  $> 8 \times \text{ULN}$  irrespective of duration for subjects with elevated bilirubin at study entry or  $> 5 \times \text{ULN}$  for those with normal T bilirubin at entry,
  - Concurrent AST or ALT  $> 3 \times \text{ULN}$  and T. bilirubin  $> 5 \times \text{ULN}$  for subjects entering treatment with a normal bilirubin and up to  $8 \times \text{ULN}$  for subjects entering treatment with elevated bilirubin.

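### For HCC subjects, protocol Sections 8.1.4 and 8.2.3.1 set different limits for permanently stopping study drug after liver events, and a wrong cross-reference leaves open which limit governs

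*Protocol*

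**What the plan says.** Protocol Section 8.1.4 opens: "IMP treatment should be permanently discontinued if one or more of the following drug-related adverse events occurs". Its first item is "Any AE occurring at any time during treatment that is related to IMP and that meets the DLT criteria listed in Section 6.1.2.1". Two exceptions to that item follow. One is "Grade 2 pneumonitis which was treated and resolved according to the management guidelines in Section 8.2.3"; the other is Grade 3 or 4 endocrinopathy that resolves or is adequately controlled. Neither is hepatic and neither mentions HCC.

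Section 6.1.2.1 lists AST or ALT above 10 x ULN as criterion 6 and total bilirubin above 5 x ULN as criterion 7. Neither has a duration condition or an HCC exception.

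Section 8.2.3.1 gives liver guidance for HCC with its own stopping list: "Discontinue IMP for any drug-related liver function test (LFT) abnormality that meets the following criteria". Its four items are:
- "AST or ALT $> 10 \times \text{ULN}$ for $> 2$ weeks";
- AST or ALT above 15 x ULN for any duration;
- bilirubin above 8 x ULN if elevated at entry, or above 5 x ULN if normal at entry;
- a concurrent item: AST or ALT above 3 x ULN together with bilirubin above 5 x ULN (normal at entry) or, as worded, up to 8 x ULN (elevated at entry).

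The bullet before the list deals with re-dosing: "IMP may resume when AST or ALT have returned to near baseline unless the criteria for permanent discontinuation are reached (Sections 4.1.19 and 4.2").

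On scope, Section 8.2.3 introduces the guidance this way: "Recommended guidelines for managing hepatic events in subjects with elevated baseline LFTs are provided in Section" 8.2.3.1. The heading of 8.2.3.1 names HCC subjects, and its opening paragraph says that the entry limits "allow enrollment of subjects with AST or ALT elevations within the CTCAE Grade 2 range. For these subjects, the following guidelines are provided".

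**The concern.** A site with an HCC subject whose transaminases rise above 10 x ULN for a short time finds one section that ends treatment and another whose HCC-specific list is not met. The sentence that permits re-dosing defers to permanent-discontinuation criteria, but it sends the reader to places where none are set out.

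What is at stake is re-dosing after a serious liver event in a population with impaired liver function, or the reverse: permanently stopping a subject whom the HCC guidance would have kept on treatment. Different sites could follow different rules. Safety and tolerability are the primary endpoint, so the rule for permanent discontinuation should be unambiguous.

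**Working it through.** No sample size, power or event count is involved. The check sets the two stopping rules side by side and follows the reference.

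**Step 1. Compare the limits for a related event in an HCC subject.** Criterion numbers are those of Section 6.1.2.1.

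| Event | 8.1.4 via 6.1.2.1 | 8.2.3.1 list | Same result? |
|---|---|---|---|
| AST/ALT >15 x ULN, any duration | Stop (6) | Stop | Yes |
| AST/ALT >10 x ULN for >2 weeks | Stop (6) | Stop | Yes |
| AST/ALT >10 to 15 x ULN for 2 weeks or less | Stop (6) | Not met on AST/ALT | **No** |
| Bilirubin >5 x ULN, normal at entry | Stop (7) | Stop | Yes |
| Bilirubin >8 x ULN, elevated at entry | Stop (7) | Stop | Yes |
| Bilirubin >5 to 8 x ULN, elevated at entry | Stop (7) | Not met on bilirubin alone | **No** |

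The third row assumes that no bilirubin or concurrent item is also met. In the last row, the concurrent item could apply if AST or ALT also exceeds 3 x ULN, depending on how its limit of up to 8 x ULN is read. The re-dosing sentence speaks only of AST and ALT, so the bilirubin row is a disagreement about stopping, not about resuming.

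**Step 2. Work one case.** Take entry AST 4 x ULN, normal bilirubin, then a related AST of 12 x ULN lasting 7 days.
- Section 8.1.4: 12 > 10, so criterion 6 is met and IMP stops permanently.
- Section 8.2.3.1: 12 is below 15, and 7 days is under 2 weeks, so no list item is met. IMP may resume near baseline unless the unlocated criteria apply.

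The two limits are well apart relative to entry values. Section 7.2 admits HCC subjects with AST or ALT up to 5 x ULN. From that entry value, the 8.1.4 limit is a 10/5 = 2-fold rise and the HCC any-duration limit is a 15/5 = 3-fold rise.

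**Step 3. Follow the reference.** The contents list and the headings show that Section 4.1 is the medical background, with 4.1.1 as its only subsection. Section 4.2 is the profile of the investigational products. The bodies are redacted, but headings and contents are visible, so redaction does not explain the mismatch. The same section cites 8.1.2.2 correctly for dose delay.

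**Step 4. Look for a precedence statement.** Section 8.1.4 defers to management guidance for pneumonitis by citing Section 8.2.3, but has no such clause for hepatic events. Section 8.2.3.1 neither cites 8.1.4 nor says that it replaces it.

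**Step 5. Check scope.** The guidance can be read as covering all HCC subjects (its heading), subjects with elevated baseline liver tests (8.2.3), or those who entered with Grade 2 AST or ALT (the wording before the bullets).

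**The case against.** The best defence is that a site can satisfy both sections by applying the stricter limit. The HCC list says when to stop and never says to continue below its limits. Section 8.1.4 is the one section headed as discontinuation criteria for toxicity, so it is a natural reading of the criteria that the re-dosing sentence means. This stands far enough to rule out saying that the sections give flatly opposite orders. It does not supply precedence: a specific list with higher limits invites the reading that it replaces the general rule, and no text excludes that.

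The safeguards are also real. Above 8 x ULN, Section 8.2.3.1 calls for prompt steroids, contact with the Medical Monitor within 24 hours of starting them, and consultation before IMP resumes. Before Amendment 3, therefore, the worked case should not have been decided by a site alone. But the Medical Monitor is not told which limit applies either. As of Amendment 3 the re-dosing decision follows site standard of care, yet Section 9.5 still has treatment given as specified in Section 8.1, which contains 8.1.4. The problem is reduced, not removed.

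A reader might infer more than the documents support:
- **That the HCC list is pointless unless it replaces 8.1.4.** This needs the limit of up to 8 x ULN in the concurrent item to be rewritten as above 8. Read literally, a subject with elevated entry bilirubin, AST 4 x ULN and bilirubin 3 x ULN meets that item without meeting criterion 6 or 7.
- **That AST or ALT above 5 and up to 10 x ULN, unresolved at 14 days (criterion 5), is a further conflict.** Section 8.2.3.1 has no AST/ALT-only stopping limit there. Silence in recommended guidance does not contradict 8.1.4.
- **That major-deviation reporting under SAP Section 4.5 is compromised.** That section does not define withdrawal criteria and leaves classification to a review plan outside these documents. Protocol Section 7.5 lists discretionary reasons for removal without citing 8.1.4.

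**Conclusion.** The point holds as an unresolved question of precedence, made worse by a wrong reference. For related AST or ALT above 10 and up to 15 x ULN lasting 2 weeks or less, Section 8.1.4 requires permanent discontinuation, the HCC list does not, and the protocol does not say which governs. The same gap exists, as a stopping rule only, for bilirubin above 5 and up to 8 x ULN with elevated entry bilirubin. Scope is also unclear.

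The ceiling is the 28 planned HCC subjects in Table 12.3.1-1, taking the heading of 8.2.3.1 as the outer limit of its scope. If only those with elevated baseline liver tests are meant, the number is smaller, and the documents do not give it. The number of events in the disputed ranges is unknown. The planned response analyses are unaffected. The matter should be corrected because it concerns re-dosing after serious liver toxicity and the cure is small.

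**What to change.** Choose one; which thresholds are right is for the sponsor's clinicians.

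1. **If the HCC limits are intended:** add to Section 8.1.4 an exception stating that hepatic events in HCC subjects follow the discontinuation criteria of Section 8.2.3.1. State in both 8.2.3 and 8.2.3.1 whether this covers all HCC subjects or only those with elevated baseline liver tests. Clarify the concurrent item, for example as bilirubin above 5 x ULN if normal at entry or above 8 x ULN if elevated, if that is what is meant. Replace the faulty reference with Section 8.1.4 and the criteria listed below it.
2. **If Section 8.1.4 is intended to govern:** delete the HCC discontinuation list and cite Section 8.1.4 alone in the re-dosing sentence.

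The cost is protocol wording, by clarification letter or in the next amendment, with no added procedures or data.
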